According to RECIST v.1.1 in case of patients with a global deterioration of health status requiring discontinuation of treatment without objective evidence of disease progression at that time every effort should be made to document objective progression, even after discontinuation of treatment. The objective response status of such patients should be determined considering RECIST v.1.1 instructions. In case any efficacy assessment cannot be done, they will be considered not evaluable for response rate analysis and PFS will be censored at the date of the last tumour assessment.

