3.2. Duration of the Study

It is estimated that the patient recruitment will be completed approximately in 24 months.

All patients included will receive study therapy until radiographic or symptomatic progression, unacceptable toxicity or withdraw of the informed consent, whatever occurs first, this is the active treatment phase. Patients discontinuing the study treatment will enter the follow-up phase.

For safety reasons all patients will have a visit 30 (+/-7) days after finishing treatment with the study drugs/medications. This post-treatment visit must be performed before starting with any new anticancer therapy; however, in case the beginning of this new therapy cannot be delayed as per the investigator's judgment, the safety visit may be performed in advance, but always before starting with the new anticancer therapy.

All patients will be followed till death or data cut-off date to evaluate the OS objective.

The start date of study is the date of the first site initiation visit. The data cut-off date will be the date of last patient's death or withdraw of the informed consent or the date when there is sufficient data to achieve the primary and secondary objectives, whichever comes first. It is estimated that the final analysis could be performed approximately 30 months after the enrolment of the first patient because, considering a median OS of 12 months, it is estimated that more than 50% of death events will have occurred at that time and overall survival analysis could be performed.

The study will be considered complete following the data cut-off date and data-lock for the final analysis. Performing exploratory objectives will be independent of the date of the end of the study.

4. Study Population

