6.1.2. Secondary Efficacy Assessments

Secondary efficacy assessments are PFS, CBR, RD, and OS:

- ✓ Progression Free Survival (PFS): is defined as the time from study enrolment to the first documented progressive disease, using RECIST version 1.1., or death from any cause, whichever occurs first.
- ✓ Clinical Benefit Rate (CBR): is defined as complete response (CR), partial response (PR), or stable disease (SD) ≥ 24 weeks according to the RECIST version 1.1.
- ✓ Response Duration (RD): is defined as the time from the first documentation of objective tumour response (CR or PR) to the first documented progressive disease using RECIST version 1.1, or to death due to any cause, whichever occurs first.
- ✓ Overall Survival (OS): is defined as the time from the date of study enrolment to the date of death from any cause.

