8.2.6.2. Analysis of Secondary Endpoints

The secondary efficacy endpoints are:

Clinical Benefit Rate (CBR): A patient will be considered to have CB if the patient has a sustained complete response (CR) or partial response (PR), or stable disease (SD) ≥ 24

weeks according to RECIST v.1.1 definitions. Otherwise, the patient will be considered as not achieving CB in the CBR analysis.

CBR will be estimated by dividing the number of patients with CR, PR, or SD \geq 24 weeks by the efficacy population by treatment arm.

$$\text{Clinical Benefit Rate} = \frac{\text{Number of CRs} + \text{PRs} + \text{SD} \geq 24 \text{ weeks}}{\text{Efficacy population}}$$

The CBR will be reported, including a 95% confidence interval.

For the CBR analysis in the ITT population, patients with inadequate data for tumour assessment (e.g., no baseline assessment or no follow-up assessments) will be considered as not achieving CB in the CBR analysis.

Response Duration (RD): RD data will be censored on the date of the last tumour assessment on study for patients who do not have objective tumour progression and who have not died due to any cause while on study. Additionally, patients who start a new anti-cancer therapy prior to documented PD will be censored at the date of the last tumour assessment prior to the start of the new therapy.

RD will only be calculated for the subgroup of patients with an objective response.

Progression-Free survival (PFS): PFS data will be censored on the date of the last tumour assessment on study for patients who do not have objective tumour progression and who have not died due to any cause while on study. Additionally, patients who start a new anti-cancer therapy prior to documented PD will be censored at the date of the last tumour assessment prior to the start of the new therapy.

The analyses of PFS will be performed in the ITT and Efficacy populations. PFS time will be summarized for the ITT population using the Life tables and displayed graphically where appropriate. Confidence intervals (CIs) for the 25th, 50th and 75th percentiles of the event free time will be reported.

Overall Survival (OS): OS data will be censored on the last date the patient is known to be alive.

OS will be analysed in the ITT and Efficacy population. The median event times and 95% CIs will be estimated.

All of the above secondary analyses will be conducted at a two-sided 0.05 level of significance.

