m	
Disease assessment for all patients at baseline will include:
 
 • CT or MRI scan of the chest, abdomen and pelvis (CAP). • Bone scans will be mandatory if the patient has bone disease or if there is any suspicious of bone metastases. Any suspicious abnormalities (ie, hotspots) identified on the bone scans at baseline must be confirmed by X-ray, CT scan with bone windows or MRI. Bone lesions identified at baseline will follow the same assessment schedule as for measurable lesions. • Brain CT or MRI scan is mandatory if the patient has CNS metastases or if there is any suspicious of CNS metastases. • CT or MRI scan of any other sites of disease as clinically indicated. • Clinical assessment of superficial disease which will include photographs of all superficial metastatic lesions. 
All lesion measurements must be recorded in the eCRF. Tumour response will be assessed using RECIST v.1.1. every 8 weeks (+/- 1 week).

n	Bone scans (if applicable) will be repeated if indicated when complete response is identified in target disease or when progression in bone is suspected. Responses should be confirmed according to RECIST v.1.1 after at least 28 days.
r	Only to be performed post-study treatment if disease progression has not yet been confirmed and patients have not begun a new therapy, the tumour assessment will be performed every 8 weeks from the last tumour assessment.
s	The patients will be followed for survival until death, loss to follow-up, withdrawal of consent or study termination by GEICAM. After progression or patient is receiving other therapy, the tumour assessment will be performed according to the standard medical practice. The date of death and all treatments received by the patient after progression (according to the standard medical practice) will be collected in the eCRF.
t	At least one paraffin sample from a metastatic lesion must be sent to the sponsor-designated central laboratory to perform methylation testing and other biomarker analysis related to secondary and exploratory objectives. It is strongly recommended that the metastatic sample has been obtained after previous therapy regimen. Surgery blocks or core biopsies would be acceptable, minimal amount of tumour tissue will be specified in the SMM.

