The objective response status of such patients should be determined considering RECIST v.1.1 instructions. In case any efficacy assessment cannot be done, they will be considered not evaluable for response rate analysis and PFS will be censored at the date of the last tumour assessment.

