#### **9.2.1.2 Analysis of Secondary Endpoints**

The secondary efficacy endpoints are:

**Clinical Benefit Rate (CBR):** A patient will be considered to have CB if the patient has a sustained complete response (CR) or partial response (PR), or stable disease (SD)  $\geq 24$  weeks according to RECIST version 1.1 definitions. Otherwise, the patient will be considered as not achieving CB in the CBR analysis.

CBR will be estimated by dividing the number of patients with CR, PR, or SD  $\geq 24$  weeks by the efficacy population.

$$\text{Clinical Benefit Rate} = \frac{\text{Number of CRs + PRs + SD} \geq 24 \text{ weeks}}{\text{Efficacy Population}}$$

The CBR will be reported, including a 95% confidence interval.

For the CBR analysis in the ITT population, patients with inadequate data for tumour assessment (e.g., no baseline assessment or no follow-up assessments) will be considered as not achieving CB in the CBR analysis.

**Duration of Response (DoR):** DoR is defined as the time from the first documentation of objective tumour response (CR or PR) to the first documented PD using RECIST version 1.1, or to death due to any cause, whichever occurs first. DoR data will be censored on the date of the last tumour assessment on study for patients who do not have objective PD and who have not died due to any cause while on study. Additionally, patients who start a new anti-cancer therapy prior to documented PD will be censored at the date of the last tumour assessment prior to the start of the new therapy.

RD will only be calculated for the subgroup of patients with an objective response.

**Progression-Free survival (PFS):** PFS is defined as the time from study enrolment to the first documented PD, using RECIST version 1.1, or death from any cause, whichever occurs first. PFS data will be censored on the date of the last tumour assessment on study for patients who do not have objective PD and who have not died due to any cause while on study. Additionally, patients who start a new anti-cancer therapy prior to documented PD will be censored at the date of the last tumour assessment prior to the start of the new therapy.

The analyses of PFS will be performed in the ITT and Efficacy populations. PFS time will be summarized for the ITT population using the Life tables and displayed graphically where appropriate. Confidence intervals (CIs) for the 25th, 50th and 75th percentiles of the event free time will be reported.

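### For a patient who stops for global deterioration, is not re-imaged and then dies, the design sections censor PFS while the PFS definition and analysis sections count an event

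*Protocol*

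**What the plan says.** Two sets of passages govern PFS for a patient who stops because her general condition worsens, without objective progression at that point.

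**Design sections.** Protocol 3.1 asks for every effort to document progression after stopping. Where no assessment can be made, "they will be considered not evaluable for response rate analysis and PFS will be censored at the date of the last tumour assessment". SAP section 3 (text under Figure 1) ends on the same rule: "PFS will be censored at the date of the last tumour assessment". Neither mentions death.

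**Definition and analysis sections.** Protocol 6.1.2 ends PFS at the "first documented progressive disease, using RECIST version 1.1., or death from any cause, whichever occurs first". SAP 9.2.1.2 agrees: "PFS is defined as the time from study enrolment to the first documented PD, using RECIST version 1.1, or death from any cause". Protocol 8.2.6.2 reserves censoring at the last tumour assessment for "patients who do not have objective tumour progression and who have not died due to any cause while on study", and SAP 9.2.1.2 carries the same restriction. Both add a separate rule: a patient who starts a new anti-cancer therapy before documented progression is censored at the last assessment before that therapy.

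**Related text.** Protocol 6.1 repeats the deterioration paragraph with no PFS clause, and makes patients non-evaluable when an assessment *can* be done, where 3.1 says *cannot*. Protocol 3.2 makes this situation foreseeable: "All patients included will receive study therapy until radiographic or symptomatic progression". It also follows all patients for death until data cut-off.

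**The concern.** The design sections, read as written, censor a patient whose later death is a PFS event by definition. Both rules stand in the same SAP with no order of precedence, so whoever programs PFS has to choose. In an open-label, single-arm trial with local tumour assessment, that choice should not be left until outcomes are known.

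The censoring is also informative: patients are censored because they are getting worse, so their later course is not represented by those who stay at risk. At stake are the Kaplan-Meier PFS estimates and the Cox models relating methylation and expression to PFS.

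A neighbouring gap concerns patients with no post-baseline scan. Their last tumour assessment is the baseline one, done within 28 days before treatment (Protocol Attachment 1), while PFS runs from enrolment and treatment starts within 7 days of enrolment (Protocol 5.3). The baseline scan can precede enrolment, giving a zero or negative PFS time. SAP 7.1.1 repairs negative durations only for dates with a missing day.

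**Working it through.** **1. The rules side by side** (no new anti-cancer therapy before progression)

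| Patient who stops for deterioration | Protocol 3.1 / SAP 3 | Protocol 6.1.2, 8.2.6.2 / SAP 9.2.1.2 |
|---|---|---|
| Later scan shows progression | Clause not triggered; event | Event |
| No further scan, alive at cut-off | Censored at last scan | Censored at last scan |
| No further scan, dies | Censored at last scan | Event at death |

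Only the last row conflicts. The analysis sections limit the death condition to deaths on study. That does not rescue the design rule, because Protocol 4.4.1 separates stopping treatment from leaving the study, so a patient in survival follow-up is still on study.

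**2. No plan figure to reproduce.** The documents state no PFS target, event count or power. They give neither the share of patients affected nor the time from stopping to death. Everything below rests on assumed values.

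**3. Early deaths (assumed case).** Take 31 patients: 4 deteriorate and die before the first scan, 12 progress at the week-8 scan, 15 continue.
- Censored at baseline: 27 at risk at week 8; PFS = 15/27 = 55.6%. The median lies beyond week 8.
- Death as event: PFS = (31 − 4 − 12)/31 = 15/31 = 48.4%. The median is 8 weeks.

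Censoring raises PFS.

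**4. Late deaths (assumed case).** Take 31 patients: 12 progress at week 8; 4 are scanned at week 8, then deteriorate unscanned and die at week 20; 3 progress at week 16; 12 progress at week 24.
- Censored at week 8: 19/31 × 12/15 = 49.0% at week 16. The median is 16 weeks.
- Death as event: 16/31 = 51.6% at week 16, then 12/31 = 38.7% at week 20. The median is 20 weeks.

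Censoring lowers PFS here, because counting the death keeps these patients at risk until it occurs.

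**5. Range by time to death.** Large-sample simulation with scans every 8 weeks (Protocol 6.1.1), exponential times, and 20% of patients deteriorating unscanned and later dying (assumed). The reference medians come from Protocol Table 4: 3.68 months, and 54 days (54/30.4375 = 1.77 months). Six-month PFS, censored versus death as event:

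| Median time from stopping to death (assumed) | Reference 3.68 months | Reference 1.77 months |
|---|---|---|
| 1 month | 42.5% vs 37.0% | 15.8% vs 13.0% |
| 2 months | 42.4% vs 39.3% | 15.7% vs 16.1% |
| 4 months | 42.6% vs 42.6% | 16.2% vs 20.7% |
| 6 months | 42.5% vs 44.0% | not run |

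The gap runs from +5.5 points (42.5 − 37.0) to −4.5 points (16.2 − 20.7).

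**6. Range by share affected.** Simulated trials of 34 patients, with death on average 1 month after stopping (assumed), so only the early-death situation. Six-month PFS, censored versus death as event:

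| Share affected (assumed) | Reference 3.68 months | Reference 1.77 months |
|---|---|---|
| 5% | 37.3% vs 35.8% | 12.5% vs 11.7% |
| 10% | 38.7% vs 35.7% | 13.3% vs 11.6% |
| 20% | 43.1% vs 36.7% | 15.1% vs 11.7% |
| 30% | 46.7% vs 37.0% | 19.0% vs 12.8% |

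At 20% affected, about 27 of 34 patients count as events instead of 34. About 2 (reference 3.68 months) to 3 (1.77 months) are censored at time zero for want of a post-baseline scan.

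**The case against.** The best defence is that the analysis sections already handle death correctly, and that the clause in Protocol 3.1 and SAP section 3 is design narrative meant for patients alive without progression. For them, censoring at the last scan matches the PFS definition, since symptomatic deterioration is not a PFS event. This reading is plausible, but it is not written anywhere. It does defeat any inference that the plan discards deaths throughout.

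A reader might infer more than the documents support:

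- *That the rule always favours olaparib.* It does not. The late-death case and the longer times to death in the simulation go the other way.
- *That it removes the fastest failures from the risk set.* Strictly, this holds only for patients with no post-baseline scan. Others stay at risk until their last scan.
- *That these patients can never be recovered as events.* Protocol 3.1 asks for progression to be sought after stopping. Footnote r of Protocol Attachment 1 limits post-treatment scans, "Only to be performed post-study treatment if disease progression has not yet been confirmed and patients have not begun a new therapy", but continues them every 8 weeks otherwise. Deaths are collected for everyone. Loss after a new therapy comes from the separate censoring rule in 8.2.6.2 and SAP 9.2.1.2.
- *That the trial's decision is at risk.* PFS is one of four secondary efficacy endpoints, with no stated hypothesis or historical PFS comparator.

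The time-zero problem also arises under the analysis sections. It is a separate gap and no evidence of the contradiction.

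**Conclusion.** The conflict is real and textual. It is confined to patients who stop for global deterioration, are not re-imaged, start no new anti-cancer therapy and then die. Following SAP section 3 literally would contradict the PFS definition in SAP 9.2.1.2.

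Neither the size nor the direction can be fixed from the documents. With death about a month after stopping, censoring raises six-month PFS by 0.8 points (12.5 − 11.7, 5% affected) to 9.7 points (46.7 − 37.0, 30% affected). With 20% affected and death several months later, the difference vanishes or reverses. All of this depends on the assumed share, time to death and exponential times. The ORR decision rule and the sample size do not depend on the PFS clause.

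**What to change.** - In Protocol 3.1 and SAP section 3, replace the PFS clause with: *PFS follows Protocol 8.2.6.2 / SAP 9.2.1.2: a later documented PD or death is an event; censoring at the last tumour assessment applies only to patients with neither.* The rule there for patients who start a new anti-cancer therapy is left as it stands, and the sentence should be read subject to it.
- Align the deterioration paragraph in Protocol 6.1 with 3.1 (*cannot* in place of *can*).
- In Protocol 8.2.6.2 and SAP 9.2.1.2, state that patients alive with no post-baseline scan are censored at day 1 (enrolment).
- Optionally, add one PFS sensitivity analysis that counts discontinuation for symptomatic deterioration as an event at the stop date. This is a different endpoint from either documented rule and is not needed to resolve the conflict.

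The cost is minor wording and possibly one extra table. Death dates and treatment discontinuations are already collected, so no new data are needed. Reported PFS could move either way.

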3.1.1. Step 1 analysis of the optimal two stage Simon model

Following the two-stage Simon design, it will review that 4 of the first 12 evaluable patients show tumour response according to RECIST v.1.1, additional patients will be included to get a total of 34 patients.

3.2. Duration of the Study

It is estimated that the patient recruitment will be completed approximately in 24 months.

All patients included will receive study therapy until radiographic or symptomatic progression, unacceptable toxicity or withdraw of the informed consent, whatever occurs first, this is the active treatment phase. Patients discontinuing the study treatment will enter the follow-up phase.

For safety reasons all patients will have a visit 30 (+/-7) days after finishing treatment with the study drugs/medications. This post-treatment visit must be performed before starting with any new anticancer therapy; however, in case the beginning of this new therapy cannot be delayed as per the investigator's judgment, the safety visit may be performed in advance, but always before starting with the new anticancer therapy.

All patients will be followed till death or data cut-off date to evaluate the OS objective.

The start date of study is the date of the first site initiation visit. The data cut-off date will be the date of last patient's death or withdraw of the informed consent or the date when there is sufficient data to achieve the primary and secondary objectives, whichever comes first. It is estimated that the final analysis could be performed approximately 30 months after the enrolment of the first patient because, considering a median OS of 12 months, it is estimated that more than 50% of death events will have occurred at that time and overall survival analysis could be performed.

The study will be considered complete following the data cut-off date and data-lock for the final analysis. Performing exploratory objectives will be independent of the date of the end of the study.

4. Study Population

4.1. Inclusion Criteria

Patients are eligible to be included in the study only if they **meet all** of the following criteria. Any asterisked* are also applicable as an inclusion criteria prior to perform the BRCA methylation testing via central testing; to perform the *BRCA* methylation test, investigator judgement of patient's potential eligibility to the study should be assessed as per Protocol Attachment 1. Study Schedule and by reviewing the below inclusion criteria):

1. *The patient has signed and dated the informed consent document and it has been obtained before conducting any procedure specifically for the study.
2. Female ≥ 18 years of age on day of signing informed consent.
3. Patient with histological confirmation of breast cancer with evidence of advanced disease not amenable to resection or radiation therapy with curative intent.
4. Documented **triple negative** disease by immunohistochemistry (IHC) and/or *in situ* hybridization based on local testing (preferably assessed on the most recent tumour biopsy available). TN is defined as **negative hormone receptor status** ($< 1\%$ of tumour cells with ER and PgR expression) and **HER2-negative status** (defined as IHC score 0/1+ or negative by *in situ* hybridization according to local criteria).
5. Patient must have received at least one previous regimen in the advance disease setting.
6. Absence of deleterious or suspected deleterious germline mutations in *BRCA1* and *BRCA2*. Germinal *BRCA* mutational status will be centrally assessed in Myriad laboratories to check eligibility unless the test has been previously performed at Myriad and absence of mutations has been determined.
7. Availability of a tumour tissue sample from the metastatic lesions (every effort should be done to obtain the sample after the previous therapeutic regimen for advanced disease) for central testing.
8. Documented methylation of *BRCA1* and/or 2 promoters based on central testing by analysis on the most recent tumour from metastatic lesions available.
9. At least one lesion measurable not previously irradiated, that can be accurately measured at baseline as ≥ 10 mm in the longest diameter (except lymph nodes which must have short axis ≥ 15 mm) with computed tomography (CT) or magnetic resonance imaging (MRI) or clinical examination and which is suitable for accurate repeated measurements according to RECIST v.1.1.
10. Patients must have normal organ and bone marrow function measured within 28 days prior to administration of study treatment as defined below:

- Haemoglobin ≥ 10.0 g/dL with no blood transfusions in the past 28 days
- Absolute neutrophil count (ANC) $\geq 1.5 \times 10^9$ /L
- Platelet count $\geq 100 \times 10^9$ /L
- Total bilirubin $\leq 1.5 \times$ institutional upper limit of normal (ULN)
- Aspartate aminotransferase (AST) (Serum Glutamic Oxaloacetic Transaminase, SGOT) /Alanine aminotransferase (ALT) (Serum Glutamic Pyruvate Transaminase, SGPT)] $\leq 2.5 \times$ institutional upper limit of normal unless liver metastases are present in which case, they must be $\leq 5 \times$ ULN
- Patients must have creatinine clearance estimated using the Cockcroft-Gault equation of ≥ 51 mL/min:

$$\text{Estimated creatinine clearance} = \frac{(140 - \text{age [years]}) \times \text{weight (kg)}}{\text{serum creatinine (mg/dL)} \times 72}$$

^a where F=0.85 for females.

11. *Eastern Cooperative Oncology Group (ECOG) performance status (PS) 0-1 (see protocol attachment 2).
12. *Patient must have a life expectancy ≥ 16 weeks.
13. *Postmenopausal or evidence of non-childbearing status for women of childbearing potential: negative urine or serum pregnancy test within 28 days of study treatment and confirmed prior to treatment on day 1.
Postmenopausal patient is defined as a woman fulfilling any one of the following criteria (based on the NCCN definition of menopause [National Comprehensive Cancer Network 2008]):
 - Prior bilateral oophorectomy.
 - Age > 60 years.
 - Age ≤ 60 years and with amenorrhea for 12 or more months in the absence of chemotherapy, tamoxifen, toremifene, or ovarian suppression and follicle stimulating hormone and estradiol in the postmenopausal range.
14. Olaparib is regarded as a compound with medium/high foetal risk, patients of childbearing potential and their partners, who are sexually active, must agree to the use of TWO highly effective forms of contraception in combination as listed below. This should be started from the signing of the informed consent and continue throughout period of taking study treatment and for at least 1 month after last dose of study drug or they must totally/truly abstain from any form of sexual intercourse (see below).

Acceptable non-hormonal birth control methods include:

- Total sexual abstinence. Abstinence must continue for the total duration of the study treatment and for at least 1 month after one dose. Periodic abstinence (e.g., calendar ovulation, symptothermal, post-ovulation methods) and withdrawal are not acceptable methods of contraception.
- Vasectomised sexual partner PLUS male condom. With participant assurance that partner received post-vasectomy confirmation of azoospermia.
- Tubal occlusion PLUS male condom.
- Intrauterine Device (IUD) PLUS male condom. Provided coils are copper-banded.

Acceptable hormonal methods:

- Normal and low dose combined oral pills PLUS male condom.
- Cerazette (desogestrel) plus male condom with spermicide. Cerazette is currently the only highly efficacious progesterone based pill.
- Hormonal shot or injection (e.g., Depo-Provera) PLUS male condom.
- Etonogestrel implants (e.g. Implanon or Norplan) PLUS male condom.
- Norelgestromin/ethynodiol dihydrogen phosphate (EDHP) transdermal system PLUS male condom
- Intrauterine system (IUS) device (e.g., levonorgestrel releasing IUS-Mirena®) PLUS male condom.
- Intravaginal device PLUS male condom (e.g. EE and etonogestrel).

14. *Patient is willing and able to comply with the protocol for the duration of the study including undergoing treatment and scheduled visits, laboratory tests and examinations and other study procedures.

